### **2.2 Study Endpoints**

Data obtained from the use of the current standard-of-care (Stage 1) and of B. Braun PA (Stage 4) will be used in the assessment of the Primary and Secondary Endpoints.

#### **2.2.1 Primary Endpoint**

The primary endpoint for this study is the rate/percentage of complications (e.g., phlebitis/thrombophlebitis, occlusion, infection (localized or Catheter Related Bloodstream Infection (CRBSI), dislodgement or infiltration, extravasation, accidental removal, etc.).

#### **2.2.2 Secondary Endpoint**

The secondary endpoints for this study are:

- Indwell time for catheters with and without complications (measured in hours)

- First attempt insertion success rate (first stick success) for PIVC
- Rate of insertion of a Peripherally Inserted Central Catheter (PICC) or Midline Catheter due to inability to insert the PIVC or removal of the initial PIVC due to complications (rescue PICC or rescue Midline)
- Impact of using B. Braun PA on the healthcare costs associated with PIVC use in a clinical setting.

### **3 INVESTIGATIONAL PLAN**

#### **3.1 Study Design**

This is a single sequence study to evaluate the effectiveness of B. Braun PA on improved clinical outcomes by decreasing PIVC complications, increasing PIVC indwell time, improving first PIVC stick success and improving estimated aggregated costs utilizing B. Braun PA.

The study will be divided into 4 Stages: 3 Clinical Stages and 1 Interventional (Educational) Stage. These 4 Stages are: Baseline (Stage 1), Intervention (Stage 2, education), Run-In (Stage 3), and Post-Interventional (Stage 4). The 3 clinical Stages (Baseline, Run-In, and Post-Interventional) require patient care which includes daily follow-up care for the catheter. The Intervention (education) Stage (Stage 2) may include all RNs from the medical surgical floor(s)/unit(s) of the hospital/hospital network. This training in B. Braun PA will not involve any patients.

The study will be conducted in the medical surgical floor(s)/unit(s) of multiple individual hospitals. Patients from the Emergency Department (ED) are also eligible to be enrolled. Any RNs from these floors or the hospital ED are eligible to participate in Stage 1 of the study. After completion of protocol training and any required site specific training (GCP, consent process, etc.) to the RNs will be considered Study RNs. The Study RNs from Stage 1 and any other RNs from the medical surgical floor(s)/unit(s) or the hospital ED who complete protocol training may participate in the intervention (Stage 2). The Study RNs on all shifts who have completed the protocol training/intervention (Stage 2) will participate in Stage 3 and Stage 4 of the study. All Study RNs will be responsible for PIVC insertions and catheter examinations. Non-Study RNs should not perform any study related procedures (i.e., catheter insertion, insertion site examinations including documentation of both positive and negative findings, and catheter removal). In the event all RNs from the participating department(s)/unit(s) and ED are not able to participate in the study, the Investigator will take reasonable measures to ensure all study-related procedures are performed by the Study RNs.

A minimum of 632 successful PIVC placements are required to complete the study (316 successful PIVC placements in Stage 1 and 316 successful PIVC placements in Stage 4). Each study Stage must be completed before proceeding to the next study Stage. The final sample sizes of Stage 1 and Stage 4 will be determined by the 2 interim analyses.

The study will be conducted in compliance with this protocol, GCP, and any other applicable regulatory requirements.

### **3.2 Study Population: Registered Nurses and Subjects**

Data obtained from all subjects who enroll in any Stage of the study and from the Study RNs will be included in analysis of safety and the study endpoints.

#### **3.2.1 Registered Nurses**

Only Study RNs from the medical surgical unit(s) or within the ED of the hospital will perform study-related procedures. Registered nurses can be on any shift(s) and will not be required to have a minimum level of clinical experience. Any Study RN who does not complete all of the B. Braun trainings in Stage 2 cannot continue on to Stages 3 and 4 and thus is removed from participation in the study. Years of experience and other demographic information will be collected from the Study RNs in Stage 1 and any RNs who join the study in Stage 2. Study RNs participating in Stage 1 or joining the study in Stage 2 should not be currently using the B. Braun Introcan Safety® IV Catheters and/or the STEADYCare™ Smallbore Extension Set utilized in this study.

#### **3.2.2 Subjects**

Subjects will be enrolled into the study to ensure there are at least 632 successful PIVC placements, with at least 316 successful PIVC placements in Stage 1 and 316 successful PIVC placements in Stage 4. In Stage 3, Study RNs will familiarize themselves with B. Braun devices in a clinical setting by using them exclusively as standard-of-care for PIVC patients. Stage 3 does not require a statistically defined number of PIVC placements and will run for about 3 weeks. During this time it is anticipated that each Study RN will perform approximately 10 insertions ([Reznek 2002](#)).

Subjects or his/her LAR (if appropriate) will provide consent before participating in Stage 1 (Baseline) and Stage 4 (Post-Interventional) and may participate in one, or both, of those stages. Subjects consented for Stage 1 may participate as patients in Stage 3 (Run-In). A subject who previously or currently has a catheter inserted due to medical need may participate in the study if he/she or his/her LAR (if appropriate) provides consent. However, consent must be given before any study-related procedures including the replacement of a catheter utilizing the hospital's standard-of-care (Baseline Stage 1) or B. Braun PA (Post-Intervention Stage 4). The replacement catheter must be inserted in a different arm (see Exclusion criteria 5 below).

Subjects will be classified as 1 or more of the following based on their individual participation in the study:

- Screen Failure: Any subject who signed the Informed Consent or who's LAR provided consent and then the subject failed to meet the inclusion and or exclusion criteria,
- Enrolled: Any subject who signed the Informed Consent or who's LAR provided consent and then the subject met all of the inclusion and exclusion criteria,
- Early Termination: Any subject who was Enrolled but never had an attempted PIVC insertion or who was Enrolled and did not have a successful PIVC insertion by a study RN,

- Early Withdrawal: Any subject who was Enrolled, but who voluntarily withdrew their consent or was withdrawn by their LAR or was withdrawn by the PI,
- Study Completer: Any Enrolled Subject who had a successful PIVC insertion by a Study RN and had the PIVC removed for any reason

#### **4 SELECTION AND DISCONTINUATION OF TREATMENT**

RNs must complete all of the required B. Braun trainings in Stage 2 in order to participate in Stages 3 and 4.

##### **4.1 Inclusion Criteria**

Subjects must meet all of the following Inclusion Criteria:

1. Male or female aged  $\geq 18$  years;
2. The subject or the subject's LAR voluntarily agrees that the subject will participate in this study and is able to understand and sign the Informed Consent Form (ICF);
3. Have a medical condition that requires a PIVC anticipated to last for at least 48 hours;
4. Have intact skin at the site of insertion;
5. If the patient has an existing IV in one arm he/she must have a viable contralateral arm for additional PIVC insertion.

##### **4.2 Exclusion Criteria**

Subjects must not meet any of the following Exclusion Criteria:

1. Are currently participating in another medical device or pharmaceutical study;
2. In the opinion of the Investigator, would not be suitable candidates for this study;
3. The subject or his/her LAR is an employee of the Investigator or study center or sponsor, have direct involvement in the study or other studies under the direction of that Investigator or study center, or are a family member of the employees or the Investigator;
4. Have a laboratory confirmed bloodstream infection within 48 hours prior to participation in the study. The assessment is based on clinical observations and not routine for all subjects;
5. Patient has an existing non study related IV;
6. Was removed from any Stage of the study due to an AE associated with the PIVC.

#### **4.3 Interruption or Discontinuation of Treatment**

In accordance with legal requirements and ICH-GCP guidelines, every subject has the right to refuse further participation in the study at any time and without providing a reason. A subject may also be withdrawn by his/her LAR or by the Investigator or B. Braun due to a serious protocol violation or if it is determined it is in the best interest of the subject. In the event a subject withdraws from the study before the first attempt of a PIVC insertion or has no successful stick by a Study RN, he/she will be considered as an Early Termination from the study. In the event a subject or his/her LAR withdraws consent or the PI removes the subject from the study for any reason, the subject will be considered an Early Withdrawal.

### **5 INVESTIGATIONAL DEVICE: DETAILS OF STUDY PRODUCT**

The devices in the B. Braun PA Program are all cleared for marketing or exempt from clearance by the FDA. There will be no study specific product labels.

#### **Manufacturers of Components of B. Braun Peripheral Advantage Program:**

- PIVC Education Curriculum – developed and delivered by B. Braun Medical Inc.
- Christie VeinViewer® Vision2 – manufacturer Christie Medical Holdings Inc
- Introcan Safety® IV Catheters – manufacturer B. Braun Medical Inc.
- STEADYCare™ Smallbore Extension Set with Wedge™ Catheter Stabilizer – manufacturer B. Braun Medical Inc.

#### **5.1 Description of B. Braun Peripheral Advantage Program Components**

##### **Christie VeinViewer® Vision2**

The adjustable head can be positioned over any part of the anatomy, leaving the clinician's hands free to perform the procedure, using the trademarked Eyes of Patient (EOP™) technique. The Christie VeinViewer® Vision2 unit contains the following: optical head assembly, arm, battery, battery compartment door, power module, arm lock, power cord, handle, basket, cart, cart base, wheel lock, wheel, cart base counterweight, cable clips, user guide, software (compact disc [CD]) and training video (digital versatile disc [DVD]), and universal serial bus (USB) cable. This study will utilize the optional Stability Mount (S-Mount) which allows Christie VeinViewer® Vision2 to be positioned over any part of the anatomy, leaving the clinician's hands free to perform the procedure. The Christie VeinViewer® Vision2 should be stored between -10°F to +140°F (-23°C to +60°C) and operate between +60°F to +86°F (+16°C to +30°C).

##### **Introcan Safety® IV Catheters**

The Introcan Safety® IV Catheters is designed to minimize needlestick injuries and has been available in the US since 2002. This device is made of polyurethane (PUR), polypropylene (PP), acrylonitrile-butadiene-styrene (ABS), chrome-nickel steel or fluorinated ethylene propylene (FEP). This sterile device is for single use only. The specific gauges and lengths to be supplied will be appropriate for the study facility.

##### **STEADYCare™ Smallbore Extension Set with Wedge™ Catheter Stabilizer**

The STEADYCare™ Smallbore Extension set is comprised of the STEADYCare™ Smallbore Extension Set with Wedge™ Catheter Stabilizer, Female Luer Lock Connector, and Spin-Lock® Connector. This sterile device is for single use only.

## 5.2 Product Handling and Accountability

Only study related supplies provided by B. Braun will be used by Study RNs on patients/subjects participating in Stages 3 and 4. These Study RNs will be the only personnel tasked with study related PIVC insertions/removals and assessing for complications on their associated units. During Stages 3 and 4, Study RNs will only utilize the B. Braun Peripheral Advantage products. In the event that standard-of care products are still available alongside B. Braun study-related supplies in this unit(s), the Investigator or designee will take appropriate measures to ensure study subjects receive only the B. Braun devices. B. Braun products supplied for this study are not to be used for patients outside of the unit/department(s) in which this study is being conducted. Study related supplies must be stored as per Hospital/Hospital Network SOP's and guidelines as well as the conditions specified on B. Braun PA labels.

The Investigator or a designee must maintain a complete record of the shipment and receipt of B. Braun PA in an accountability log. This log must be kept current and should contain at least the date and amount received, lot number (s), and expiration date(s). Whenever a B. Braun PIVC device is used for a study subject in Stage 4, the use will be recorded in the eCRF and on the accountability log. In the event any B. Braun PIVC devices are inadvertently used by Study RNs for non-study patients in the participating ED or medical/surgical department(s)unit(s), no study related information will be recorded. The use of B. Braun PA for non-study patient standard-of-care will be recorded in the accountability log.

During the course of the study, the used Introcan Safety® IV Catheters and the used STEADYCare™ Smallbore Extension Set must be disposed of in accordance with hospital policy and local regulations governing the disposal of medical and/or hazardous waste. If a device fails at any point during the study, it must be returned to B. Braun in accordance with B. Braun SOPs for device malfunction/return. The Christie VeinViewer® Vision2 will be returned to B. Braun at the conclusion of the study, unless otherwise agreed upon in writing. Unused Introcan Safety® IV Catheters and unused STEADYCare™ Smallbore Extension Sets will be retained or destroyed by the study site per their internal policies.

When requested in writing by B. Braun, unused study related supplies must be destroyed by the Investigator, provided such disposition does not expose humans to risks. Records shall be maintained by the Principal Investigator of any such alternative disposition of the investigational devices. These records must show the identification and quantity of each unit disposed of, the method of destruction (taking into account the requirements of local law), and the person who disposed of the study related supplies. Such records will be maintained in the Study File.

## 5.3 Product Storage

The Christie VeinViewer® Vision2 is to be stored/retained in the unit/department(s) where the study is being conducted.

The Introcan Safety® IV Catheters and the STEADYCare™ Smallbore Extension Set are also to be stored in the unit/department(s) in which the study is being conducted. If there is insufficient space on this floor to store all the IV associated products received, it is acceptable to store the remaining IV associated supplies in a limited access/secure area separate from the study floor. These materials must be clearly identified as to be used only for B. Braun study US-N-H-1801.

The Introcan Safety® IV Catheters and the STEADYCare™ Smallbore Extension Set must be used prior to the expiration dates noted on the package labels.

To assure that only the Study RNs complete the subject PIVC insertions using the Introcan Safety® IV Catheters, the STEADYCare™ Smallbore Extension Set and the Christie VeinViewer® Vision2, these products will be stored in a separate locked area. Access to this restricted area will be provided only to the appropriate study staff. Use of study related products will be documented on the accountability log and, for consented subject, in the eCRF.

The Sponsor will provide product with a shelf life of approximately one (1) year.

#### **5.4 Package Labeling**

The devices in the B. Braun PA Program are all currently cleared for marketing or exempt from clearance by the FDA. There will be no study specific product labels.

[figure not shown]
### **6 STUDY VISIT AND ASSESSMENTS**

This study will be conducted in the ED or medical surgical unit/departments. Only participating Study RNs will perform study related procedures. Baseline demographic/clinical experience information from RNs will be obtained. This information will include age, gender, title/function, shift, and years of clinical experience.

Subjects must have a medical condition requiring IV treatment through a PIVC anticipated to last for at least 48 hours. A subject may participate in one or more of the 3 Stages that require patient care (Baseline, Run-In, and Post-Interventional).

A study flow diagram outlining the main study procedures is shown in [Figure 1](#).

Figure 1 **Study Flow Diagram**

### **6.1 Stage 1: Baseline**

Any RNs from the participating floors or the hospital ED are eligible to participate in Stage 1 of the study and after completion of protocol training and any required site specific training (GCP, consent process, etc.) will be considered Study RNs.

Subjects or their LAR who are consented by a Study RN and who meet all the inclusion and none of the exclusion criteria will be able to participate in this Stage. At least 316 successful PIVC placements are required in the Baseline Stage. During this Stage, Study RNs will continue with their routine standard-of-care with regard to PIVC insertion technique and continue using the Institution's standard PIVC product. The catheter brand, insertion site location, characteristics, number of attempts, dressing condition, complications and removal information (length of indwell time in hours and reason for removal) will be recorded in the electronic Case Report Form (eCRF) for each insertion attempt. In addition, the catheter and site of insertion will be examined daily and any relevant clinical findings will be recorded in the eCRF. The subject's baseline demographic data (age, gender) will be collected. If the attempts fail and the subject requires a different catheter, such a PICC, Midline or Central Catheter, or a PIVC from a different manufacturer will be recorded in the eCRF.

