## 8 DEVICE REMOVAL

It is expected that the Study RNs will evaluate the catheter site before the catheter is removed. Once the catheter is removed by the Study RN, Standard facility protocols will be followed for catheter removal and the dressing of the IV site. The dressing of the IV site may be performed by a non-study nurse, however the date and time of removal and the reason for removal must be recorded.

A catheter may be removed at the end of a subject's medical treatment, as a result of complications or for any other reason determined by the treating clinician. If PIVC therapy is still required after catheter removal, the subject may continue to receive PIVCs in accordance with his/her treating physician. If the PIVC was removed as a result of complications, the subject may not continue in or re-enter the study and will be considered a Study Completer. Complications will be assessed as potential Adverse Events (AEs) as described in [Section 11](#). If the PIVC was removed as a result of treatment completion (i.e., subject no longer requires a PIVC) he/she will be considered a Study Completer. In addition, if he/she was subsequently discharged from the facility, then he/she may re-enter the study in the same or different Stage if a re-admission for any reason is required.

The Study RN or designee will record in the eCRF if the PIVC was removed at any time due to any of the following complications: phlebitis/thrombophlebitis, occlusion, infection (localized or Catheter Related Bloodstream Infection [CRBSI]), dislodgement or infiltration, extravasation, or accidental removal. If it is medically appropriate for the subject, the PIVC may also be removed due to other conditions(s). The subject may continue to receive PIVC catheters in accordance with his/her medical treatment. If the PIVC was removed for a complication, then the subject may not continue or re-enter into the study and he/she is considered a Study Completer. Complications will be assessed as potential AEs as described in [Section 11](#).

If the PIVC was removed as a result of treatment completion (i.e., subject no longer requires a PIVC) he/she will be considered a Study Completer. In addition, if he/she was subsequently discharged from the facility, then he/she may re-enter the study in the same or different Stage if a re-admission for any reason is required.

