## 11 ADVERSE EVENTS AND SERIOUS ADVERSE EVENTS

### 11.1 Adverse Events

Study safety will be evaluated by assessment of AEs.

The Study RNs in this study are subjected to minimal health risk from the use of the devices and are anticipated to be experienced users of PIVC devices. The subjects enrolled in this study may be exposed to the standard health risks associated with PIVC insertion. All events

related to both the standard-of-care products used in the hospital and the B. Braun PA and any required procedures will be evaluated for determination as AEs and documented on the eCRFs.

An AE is any untoward medical occurrence, unintended disease or injury or any untoward clinical signs (including an abnormal laboratory finding) in subjects, users or other persons, whether or not related to the investigational device. AEs may include, but are not limited to, premature device removal, minor and major complications, infection, thrombophlebitis, accidental needlestick injuries, and device failures (i.e., disconnection, twisted port hub, leakage, or failure of safety feature). AE collection for each subject will begin after the ICF is signed and will continue until the completion of all study procedures or until the subject withdraws consent or is withdrawn from the study.

AEs will be reported by the Investigator and the Sponsor will use the reported AE term to determine the MedDRA system organ class and preferred term. The investigator will also report the AE severity (mild, moderate, severe) and relationship of the AE to either the standard-of-care products used in the hospital or the B. Braun PA.

No exposure hazard is expected. The investigational devices were manufactured according to Good Manufacturing Practices (GMPs).

Specific guidelines for classifying AEs by intensity are provided in [Table 3](#).

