### **9.4. Secondary Endpoint Analyses**

Secondary endpoints that measure rates (e.g., first stick success and the rate of insertion of a Peripherally Inserted Central Catheter (PICC) or Midline Catheter) will be tested for significance between Stages 1 and 4 using a logistics regression while controlling the baseline characteristics such as years of nursing experience.

Both Indwell Times and Impact of using B. Braun PA on the healthcare costs associated with PIVC use will be compared between Stage 1 and Stage 4 using standard parametric tests (such as Student's t-test) or a non-parametric equivalent (such as Wilcoxon signed rank test) if parametric methods are found to be inappropriate. Appropriate regression models will likely be used to estimate the differences while controlling the baseline characteristics such as years of nursing experience.

A survival analysis by Kaplan Meier Curves between Stage 1 and Stage 4 will be performed to further understand the difference in time to any complication or failure of the unit. A catheter will be considered to have been a failure/event if it is removed due to any complication or failure of the device. It will be considered censored/non-event if it is removed as it is no longer

needed by the end of Stage 1 or Stage 4, i.e., the condition improves, or the subject is discharged from the hospital.

All secondary endpoint analyses will be performed in the MITT Population.

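### The rescue PICC/Midline endpoint counts rescues after removal for a complication, but no written step records them

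*Protocol*

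**What the plan says.** **Endpoint.** Protocol 2.2.2 defines the rate of PICC or Midline insertion "due to inability to insert the PIVC or removal of the initial PIVC due to complications (rescue PICC or rescue Midline"). The protocol synopsis, the SAP synopsis and SAP 6.3.2 use the same two-part definition.

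**Recording rule.** Protocol 6.1 (Stage 1) has a different catheter entered in the eCRF under this condition: "If the attempts fail and the subject requires a different catheter, such a PICC, Midline or Central Catheter, or a PIVC from a different manufacturer". Section 6.4 repeats the rule for Stage 4.

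**End of participation.** Protocol 8 states: "If the PIVC was removed as a result of complications, the subject may not continue in or re-enter the study". Such a subject is a Study Completer, defined in 3.2.2 as an enrolled subject who "had a successful PIVC insertion by a Study RN and had the PIVC removed for any reason". Sections 12.4 and 13.2 repeat the exit rule.

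**Data at removal.** Sections 6.1 and 6.4 ask for indwell time, complications and the reason for removal. Section 8 adds that the "Study RN or designee will record in the eCRF if the PIVC was removed at any time due to any of the following complications", followed by the list of types. None of these names the device that comes next.

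**Analysis.** SAP 9.4 tests "the rate of insertion of a Peripherally Inserted Central Catheter (PICC) or Midline Catheter" by logistic regression in the MITT population and does not restrict it to one route. SAP 9.2.3 uses collected data without imputation. Table 14.5.1 (secondary endpoints, MITT) remains on the list of outputs. SAP 10 reports that the study stopped before Stage 2 and drops the Stage 4 analyses.

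**The concern.** An endpoint with two routes needs data capture for both. Here the instruction to record a PICC or Midline is tied to the first route, failed insertion. For the second route, written observation stops at the removal, and the qualifying event can only happen afterwards. A site could follow every written step and still hold no record of a Midline placed the next day because the study PIVC had occluded.

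The SAP would nevertheless report the result under the full two-route name. A reader of Table 14.5.1 would take it as the overall need for rescue lines under standard care, when it would mainly be PICC or Midline use after failed insertion. In the design as planned, the uncaptured route is also the one on which a fall in complications would act.

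**Working it through.** The documents give no rate, sample size or power for this endpoint, so there is no stated figure to reproduce. The check sets the rules side by side and then sizes the gap.

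**Step 1. Trace each route.**

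| | Rescue after failed insertion | Rescue after removal for a complication |
|---|---|---|
| Counted in the endpoint (protocol 2.2.2, SAP 6.3.2) | Yes | Yes |
| Written instruction to record the device (protocol 6.1, 6.4) | Yes | None found |
| Participation when the device is placed | Failed attempts are the trigger, so the record is made then | Already a Study Completer (protocol 3.2.2, 8) |
| Scheduled follow-up (protocol Table 2) | Not needed | Daily catheter monitoring and AEs only; the study catheter is out |
| Look-forward window or data source | Not needed | None found |

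**Step 2. Upper bound on placements entering the second route.** Inputs: 316 Stage 1 placements and an assumed Stage 1 complication rate of 50% (protocol 12.4).

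316 × 0.50 = 158

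This is an upper bound for two reasons. The primary endpoint is any complication, and a complication need not lead to removal. The study also stopped for recruitment futility before Stage 2, so Stage 1 may have ended short of 316.

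**Step 3. Rescues outside the written rule.** The documents give no rate of PICC or Midline use after a complication removal. The range below is an assumption.

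- 2%: 158 × 0.02 = 3.2
- 5%: 158 × 0.05 = 7.9
- 10%: 158 × 0.10 = 15.8

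**Step 4. Share of all rescues that the rule would capture.** Let *c* = 0.50 be the proportion entering the second route, *f* the assumed rescue rate in it, and *g* an assumed rate of rescue after failed insertion, taken per placement for simplicity. If nothing from the second route is recorded,

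captured share = *g* / (*g* + *c* × *f*)

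| *f* | *g* = 1% | *g* = 3% |
|---|---|---|
| 2% | 0.010/0.020 = 50% | 0.030/0.040 = 75% |
| 5% | 0.010/0.035 = 29% | 0.030/0.055 = 55% |
| 10% | 0.010/0.060 = 17% | 0.030/0.080 = 38% |

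Because *c* is an upper bound, each share is a lower bound for its *f* and *g*.

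**The case against.** The strongest reply is that neither the eCRF nor the derivation rules are among the documents (SAP 13 places programming rules in separate documents), and the protocol's flow diagram is not shown. The form may carry a field for the next device. Sections 6.1 and 6.4 say that a different catheter is recorded if attempts fail; they do not say that it is recorded only then. This stands as a limit on certainty. It does not supply a written requirement that would make sites complete such a field after the subject has left the study.

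A second reply is that adverse event reporting might pick up some of these cases. Complications are assessed as potential AEs, SAEs are followed to resolution, and SAP 9.5.1 describes AE outcomes. But AE collection "will continue until the completion of all study procedures or until the subject withdraws consent or is withdrawn from the study", and nothing requires the replacement device to be recorded for an ordinary occlusion, infiltration or dislodgement. This route is partial at best.

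Third, the study stopped early. That stands and reduces the weight: there will be no Stage 4 comparison to distort, and amending section 6.4 can no longer change any data. It does not remove the issue, because SAP 10 drops only the Stage 4 analyses.

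**Conclusion.** The mismatch is in the documents. The endpoint includes rescue after removal for a complication, and no written step, window or source captures it. That component would be missing or read as no rescue, so the numerator would be understated. The rate would be biased low if these subjects stay in the MITT denominator as not rescued. If they were set to missing instead, the denominator would change too, and the coding rule that decides this is not in the documents. At planned figures up to 158 Stage 1 placements are exposed, and about 3 to 16 rescues fall outside the rule at an assumed 2% to 10%.

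Four stronger readings are tempting, and the documents do not support them:

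- **That the missing route is recorded as zero.** No text says how an absent entry is coded, and the form is not available.
- **That half of the endpoint is lost.** One of two routes is uncaptured; the share of events is unknown and, under the assumptions above, varies widely.
- **That the reported figure is simply the insertion-failure rate.** A failed insertion may be followed by a central catheter, another manufacturer's PIVC or nothing, so the captured part is a subset of insertion failures.
- **That a Stage 4 benefit would be hidden.** That held for the planned comparison, but it will not be made.

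The practical effect is confined to the Stage 1 descriptive rate.

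**What to change.** **Preferred.** For each subject whose PIVC was removed for a complication, record the next vascular access device (none, PIVC, Midline, PICC, central) and its date, taken from the chart for the same admission. State how an absent entry is coded. For Stage 1 subjects already completed, abstract this retrospectively where consent allows. If the protocol is used again, write the item into sections 6.1, 6.4 and 8. The cost is one eCRF item and brief chart abstraction, limited to subjects with a complication removal.

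**Otherwise.** Restate the endpoint in SAP 6.3.2, SAP 9.4 and Table 14.5.1 as PICC or Midline after failed PIVC insertion only, and state that the post-complication component was not collected. The cost is a sentence of text and a narrower endpoint.
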